4.4.3. Sensitivity Analyses

As a sensitivity to the proportional hazards assumption, and time of censoring, for the time to event endpoints with a follow up time of 28 days the endpoints will be calculated for an extended follow-up time up to Day 60 and analysis may be performed as per Section 4.3.2.2.

4.4.4. Supplementary Analyses

No supplementary analyses planned.

4.4.5. Subgroup Analyses

No subgroup analyses are planned.

4.5. Safety Analyses

4.5.1. Extent of Exposure

As this is a single dose study, summaries of exposure will be limited to the number of participants exposed and the number of participants with interruptions or infusion stopped early and not completed. This will be presented with participant disposition.

4.5.2. Adverse Events

Adverse events analyses including the analysis of adverse events (AEs) and Serious AEs (SAEs) will be based on GSK Core Data Standards. All adverse events reported will be treatment emergent adverse events.

A summary of the number and percentage of subjects with any adverse event, AEs related to study treatment, AEs leading to permanent discontinuation of study treatment, AE leading to dose reduction, AE leading to dose interruption/delay, any serious adverse events (SAE), SAEs related to study treatment, fatal SAEs, fatal SAEs related to study treatment will be produced.

Adverse events will be coded using the standard Medical Dictionary for Regulatory Affairs (MedDRA dictionary).

A summary of number and percentage of participants with any adverse events overall and by maximum intensity will be produced. AEs will be sorted by Preferred term (PT) in descending order. These summaries will be also provided for common ($\geq 5\%$ in either treatment group) AEs and non-serious AEs. The summary will use the following algorithms for counting the participant:

- **Preferred term row:** Participants experiencing the same AE preferred term several times with different intensities will only be counted once with the maximum grade.
- **Any event row:** Each participant with at least one adverse event will be counted only once at the maximum intensity no matter how many events they have.

The frequency and percentage of AEs (all intensities) will be summarized and displayed in two ways: 1) in descending order by PT only and 2) in descending order by System Organ Class (SOC) and PT. In the SOC row, the number of participants with multiple events under the same SOC will be counted once.

A separate summary of all non-serious and common ($\geq 5\%$ in either treatment group) AEs will be provided for study intervention-related AEs. A study intervention-related AE is defined as an AE for which the investigator classifies the possible relationship to study intervention as “Yes”. A worst-case scenario approach will be taken to handle missing relatedness data, *i.e.* the summary table will include events with the relationship to study intervention as ‘Yes’ or missing. The summary table will be displayed by PT only. All SAEs will be tabulated based on the number and percentage of participants who experienced the event as well as number of occurrences. Separate summaries will also be provided for study intervention-related SAEs and common ($\geq 5\%$ in either treatment group) SAEs. The summary tables will be displayed by PT.

A study intervention-related SAE is defined as an SAE for which the investigator classifies the relationship to study intervention as “Yes”. A worst-case scenario approach will be taken to handle missing data, *i.e.* the summary table will include events with the relationship to study intervention as ‘Yes’ or missing.

In addition the following summaries will be produced:

- Non-fatal AEs and SAEs by PT and SOC.
- Fatal AEs
- Fatal study intervention-related AEs
- AEs leading to Discontinuation
- AEs leading to Dose Interruptions

Unadjusted Relative risks with Wald confidence intervals based on observed frequencies, for the proportions of participants with common ($\geq 5\%$ in either treatment group) AEs will be calculated for otilimab versus placebo.

Relative risks will not be calculated if there are no events in either of the two treatment arms being compared. The relative risks and exact confidence interval will be plotted on log base 10 scale.

The adverse events with calculated relative risks will be presented in decreasing order as per the IDSL standard.

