5. SAMPLE SIZE DETERMINATION

For Part 2:

A sample size of 346 participants will provide approximately 80% power to detect a difference of 15% in the proportion of participants alive and free of respiratory failure at a one-sided 2.5% significance level and an assumed placebo response rate of 45%. The minimal detectable effect for this design this design is 10.6%.

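### Part 2 SAP 4.5.2: common adverse events with no cases in one arm get no between-arm estimate or interval, and the relative risks are given two different interval methods

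*SAP*

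**What the plan says.** Part 2 SAP section 4.5.2 sets out the only between-arm adverse event (AE) estimate in the plan.

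- **Measure and interval:** "Unadjusted Relative risks with Wald confidence intervals based on observed frequencies".
- **Eligible events:** those reaching 5% "in either treatment group) AEs will be calculated for otilimab versus placebo".
- **Exclusion:** "Relative risks will not be calculated if there are no events in either of the two treatment arms being compared".
- **Plot:** "The relative risks and exact confidence interval will be plotted on log base 10 scale".
- **What is shown:** "The adverse events with calculated relative risks will be presented in decreasing order as per the IDSL standard".

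The same section keeps the descriptive tables: "The frequency and percentage of AEs (all intensities) will be summarized and displayed in two ways", by preferred term and by system organ class with preferred term. There are separate summaries of common AEs, serious AEs, related AEs and fatal AEs. Table 1 of the Part 2 SAP gives frequency and percentage as the summary measure for AEs and serious AEs. No risk difference, continuity correction or one-sided bound is planned for an AE with an empty arm. The Part 1 SAP (section 5.5.2) has the same exclusion and the same pair of interval methods.

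**The concern.** The word *either* in the exclusion can mean *one or the other* or *both*. Within this display only the first meaning has any effect, because the 5% entry rule means that at least one arm has cases. The sentence therefore removes the estimate from one kind of event only: none in one arm and 5% or more in the other. For a given number of cases in the affected arm, that is the most lopsided split possible.

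A Wald relative risk is not defined with an empty cell, so leaving it out is understandable. The gap is that nothing takes its place. A reader of the comparative display would see an estimate for a weaker imbalance and none for a stronger one with the same count in the affected arm. The rule works in both directions: events absent on otilimab lose their estimate too.

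The interval wording is a second, separate problem. Wald and exact are different methods, and the section does not say which one is meant for a given relative risk.

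**Working it through.** **Inputs.** Total sample size 346 (Part 2 SAP section 5); 1:1 allocation (protocol section 8.2); 5% entry rule (Part 2 SAP 4.5.2). Assumption: all 346 are dosed, so n = 173 per arm.

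**1. Reproduce the plan's figure.** The SAP states "A sample size of 346 participants will provide approximately 80% power to detect a difference of 15% in the proportion of participants", at a "one-sided 2.5% significance level and an assumed placebo response rate of 45"%. With pooled variance under the null and p̄ = (0.45 + 0.60)/2 = 0.525:

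n per arm = [1.96·√(2·0.525·0.475) + 0.842·√(0.45·0.55 + 0.60·0.40)]² / 0.15² = 172.8, rounded up to 173, or 346 in total. Power at 173 per arm is 80.0%. The plan's figure holds.

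**2. Threshold.** 0.05 × 173 = 8.65, so an event enters the display at 9 participants in one arm.

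**3. When the exclusion acts.** Entry requires at least 9 cases in one arm, so 0 against 0 cannot occur. The only tables affected are x against 0 with x ≥ 9.

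**4. Smallest excluded table, 9/173 against 0/173.**
- The relative risk is infinite, and the Wald standard error contains 1/0.
- Fisher exact two-sided p = 0.0035.
- Risk difference = 9/173 = 5.2 points.
- Score (Miettinen-Nurminen) limits are the values d that solve |0.0520 − d| / √{[p̃₁(1 − p̃₁)/173 + p̃₀(1 − p̃₀)/173]·346/345} = 1.96, where p̃₁ = p̃₀ + d are the constrained estimates. At both limits p̃₀ = 0.
- At d = 0.0276: √(0.0276·0.9724/173·346/345) = 0.0125, and (0.0520 − 0.0276)/0.0125 ≈ 1.96.
- At d = 0.0960: the standard error is 0.0224, and (0.0960 − 0.0520)/0.0224 ≈ 1.96.
- The 95% CI is 2.8 to 9.6 points. A Newcombe interval gives 1.9 to 9.6. An interval is available; it is simply not planned.

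**5. Comparison at 173 per arm.** For y > 0, RR = x/y and SE(log RR) = √(1/x + 1/y − 2/173). For 9 against 3 the SE is 0.658, so the interval is 3.0·exp(±1.96·0.658) = 0.83 to 10.9.

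| Split | Fisher p | Relative risk (Wald 95% CI) under the plan |
|---|---|---|
| 12 vs 0 | 0.0004 | none |
| 9 vs 0 | 0.0035 | none |
| 9 vs 1 | 0.020 | 9.0 (1.15 to 70.3) |
| 9 vs 3 | 0.14 | 3.0 (0.83 to 10.9) |
| 9 vs 5 | 0.41 | 1.8 (0.62 to 5.3) |

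**6. How often.** P(excluded) = P(at least 9 in one named arm) × P(0 in the other).
- Both true rates 5%: 0.4997 × 0.95¹⁷³ = 0.4997 × 0.00014 = 0.00007. A row removed this way would seldom be noise.
- 5% against 1%: 0.4997 × 0.1757 = 9%.
- 8% against 0.5%: 0.941 × 0.420 = 40%.

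These true rates are assumptions; the documents give none. The last two imply true ratios of 5 and 16.

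**The case against.** A reader might infer that the plan hides its strongest safety signals. The documents do not support that, for several reasons.

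- **The imbalance is still tabulated.** A 9 against 0 event would appear as 5.2% against 0% in the AE tables and in the common-AE summary. AEs of special interest are listed individually whatever their number (section 4.5.2.1). What is lost is the estimate and its interval. This stands in full.
- **Excluded rows are the most extreme ratios, not always the strongest evidence.** At 173 per arm, 20 against 5 (p = 0.0029) and 40 against 15 (p = 0.0003) both get a relative risk, and both have smaller p-values than 9 against 0. This stands.
- **The case is narrow.** It needs a preferred term at 5% or more in one arm and none in the other, and nothing in the documents shows that a particular term is at risk. This stands; affected rows should be few.
- **Safety is descriptive.** Protocol section 8.4.5 tests no formal safety hypothesis, and the data monitoring committee reviews unblinded safety data separately (section 8.5). No decision rule rests on this display.
- **The population is only partly new.** Part 1 enrolled patients up to 79, so by age only those aged 80 and over are new.
- **The plot's layout is not fully visible.** The SAP introduction leaves display specifications to a separate programming document. That zero-arm events drop out of the plot is the likely reading of "The adverse events with calculated relative risks will be presented in decreasing order as per the IDSL standard", but it is not stated outright. Nor does the section say that relative risks will be tabulated with Wald intervals beside a plot with exact ones; it names one method for the calculation and another for the plot.

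None of this removes the core point. A written rule, rather than missing detail, takes away the between-arm estimate for these events, and nothing replaces it.

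**Conclusion.** The point holds as a minor reporting gap. In Part 2 SAP 4.5.2 the exclusion can act only on common AEs with no cases in one arm and at least 9 of about 173 in the other. Those events keep their counts and percentages, get no between-arm estimate or interval, and would probably be absent from the relative-risk plot, while weaker imbalances with the same number of cases in the affected arm are estimated. The naming of both Wald and exact intervals for the same relative risks is a separate wording conflict that needs settling in any case.

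The threshold of 9 and the p-values rest on all 346 participants being dosed and split evenly. That the rule acts only on a single empty arm does not depend on the numbers; it follows from the 5% entry rule. The primary analysis is unaffected.

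**What to change.** In Part 2 SAP 4.5.2:

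1. Replace the exclusion with a rule that a common AE with no cases in one arm stays in the comparative display, showing per-arm counts and a risk difference with a score (Miettinen-Nurminen) 95% CI, with the relative risk marked as not estimable.
2. Name one interval method for relative risks and use it for both the calculation and the plot.

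The relative-risk display and its ordering can otherwise stay. Switching every common AE to risk differences and re-sorting by them would be a preference for another effect measure and is not needed to close the gap.

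Cost: a few sentences of SAP text and a small departure from the sponsor's standard display. No new data are needed. Risk differences are already planned in this SAP for the efficacy endpoints (section 4.2.2) and for COVID-19 signs and symptoms (section 4.4.1.13), so the measure is not new to the plan.

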8.4.5. Safety Analysis

For safety data, no formal hypotheses will be tested. Occurrence of AEs, SAEs, and AESIs, including laboratory tests, vital signs, and 12-lead ECGs will be displayed in the form of listings, frequencies, summary statistics, graphs, and statistical analyses where appropriate. Interpretation will be aided by clinical expertise. Full details, including example outputs, will be documented in the analysis plan.

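### A common adverse event seen in only one arm gets no effect estimate or interval in the SAP's only between-arm adverse-event comparison

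*SAP*

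**What the plan says.** Part 2 SAP section 4.5.2 describes the comparison of common AEs in a few consecutive sentences. The method is "Unadjusted Relative risks with Wald confidence intervals based on observed frequencies", restricted to AEs with an incidence of at least 5% in either group; "AEs will be calculated for otilimab versus placebo". The exclusion follows: "Relative risks will not be calculated if there are no events in either of the two treatment arms being compared". For the graph, "The relative risks and exact confidence interval will be plotted on log base 10 scale". On ordering, "The adverse events with calculated relative risks will be presented in decreasing order as per the IDSL standard". No continuity correction, risk difference or other zero-cell method is given. Part 1 SAP section 5.5.2 contains the same exclusion.

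The incidence tables carry no such restriction: "The frequency and percentage of AEs (all intensities) will be summarized and displayed in two ways", by preferred term and by system organ class with preferred term. Protocol section 8.4.5 sets the status of these outputs: "For safety data, no formal hypotheses will be tested".

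**The concern.** A relative-risk display lets a reader see quickly which AEs differ between arms and how precisely the difference is estimated. Under the stated rule, AEs with a moderate ratio get an estimate, an interval and a rank. AEs whose observed ratio is infinite or zero get none of these. An event that is common on one arm and absent on the other is one pattern a drug effect could take, and this is where the comparison stops.

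Sections 4.5.2 to 4.5.2.3 plan no other between-arm effect estimate for AEs. The rest is counts, percentages, event characteristics and listings. What is at stake is whether the comparative output covers all common AEs.

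**Working it through.** **Inputs.** Part 2 SAP section 5: "A sample size of 346 participants will provide approximately 80% power to detect a difference of 15" percentage points, one-sided 2.5%, placebo response 45%. SAP section 1.2: 1:1 randomisation. SAP section 4.5.2: the 5% threshold, the Wald method and the exclusion.

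**Arm size, reproducing the plan's figure.** Pooled-variance formula without continuity correction, mean rate (0.45 + 0.60)/2 = 0.525:

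n per arm = [1.960 × √(2 × 0.525 × 0.475) + 0.8416 × √(0.45 × 0.55 + 0.60 × 0.40)]² / 0.15² = (1.384 + 0.588)² / 0.0225 = 172.8, so 173 per arm and 346 in total. Power at 173 per arm is 80.05%. The stated figure reproduces.

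**When the exclusion can act.** 0.05 × 173 = 8.65, so an AE is common from 9 events (9/173 = 5.2%). Every AE in scope has at least 9 events in one arm. Zero in both arms is impossible, which leaves zero in exactly one arm.

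**What the Wald method gives there.** SE(log RR) = √(1/a − 1/173 + 1/b − 1/173), with a and b the event counts. If either is 0, a reciprocal is undefined and log RR is infinite. The planned method has no result even if the exclusion sentence were deleted.

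**The smallest affected contrast, 9 v 0.**
- Risk difference: 9/173 − 0 = 0.0520.
- Wilson limits: 0.0276 to 0.0959 for 9/173; 0 to 0.0217 for 0/173.
- Newcombe lower limit: 0.0520 − √[(0.0520 − 0.0276)² + 0.0217²] = 0.019.
- Newcombe upper limit: 0.0520 + √[(0.0959 − 0.0520)² + 0²] = 0.096.
- Two-sided Fisher p = 0.0035.
- Score-type 95% lower limit for the relative risk: about 2.4. The upper limit is unbounded.

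**The neighbouring contrast, 9 v 1.** RR = 9.0; SE(log RR) = √(1/9 − 1/173 + 1 − 1/173) = 1.049; Wald 95% CI = exp(2.197 ± 1.96 × 1.049) = 1.2 to 70.3; Fisher p = 0.020. This weaker contrast is estimated, plotted and ranked.

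**A larger affected contrast, 15 v 0.** Risk difference 8.7 points, Newcombe 95% CI 4.7 to 13.8, Fisher p = 0.00004. No relative risk is planned.

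**How often, under assumed rates.** The documents give no AE rates, so these are illustrations. For a true otilimab rate of 7%, the chance of at least 9 events on otilimab and none on placebo is P(X ≥ 9 | 173, 0.07) × (1 − placebo rate)^173:

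| Assumed placebo rate | Chance |
|---|---|
| 0% | 86% |
| 0.2% | 61% |
| 0.5% | 36% |
| 1% | 15% |
| 2% | 2.6% |

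With equal true rates of 1%, 2%, 3% or 5% in both arms, the chance of such a pattern in either direction is below 0.1% per AE. An AE that meets the rule would rarely do so by chance alone.

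**The case against.** **The wording is ambiguous.** In ordinary English, no events in *either* arm can mean that both arms are empty. On that reading the rule removes nothing. Redundancy alone does not disprove it, since section 4.5.2 also plans a summary of AEs leading to dose reduction in a single-dose study. This stands as a point about wording. It does not close the gap, because the Wald relative risk is still undefined at a zero cell and no alternative is named. The interval called exact for the plot might give a finite bound, but its method is not stated.

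**The AE is not lost.** A reader might infer that an otilimab-only event would be hidden, or that the plot would lead someone to conclude there is no imbalance. The documents do not support that. The event appears with n and % by arm in the preferred-term, organ-class, common-AE and maximum-intensity tables. AEs of special interest are always listed and get a summary above 8 events (section 4.5.2.1), so one with 9 events would have it. A 9 v 0 row is easy to see. The rule is also symmetric: placebo-only events are treated the same way.

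**Full omission from the plot is not certain.** The SAP fixes the order for AEs with a calculated relative risk. It refers to the IDSL standard, and section 1 leaves display specifications to the Output and Programming Specification. Neither is available here. A one-arm-zero AE may be printed without an estimate. What the SAP does settle is that it has no estimate, no interval and no rank.

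**Extreme only as a ratio.** On the risk-difference scale, 9 v 0 (5.2 points) is smaller than 30 v 15 (15/173 = 8.7 points). It would be wrong to say that the rule removes the largest imbalances without naming the ratio scale.

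**Plausibility.** The illustrative rates are assumptions. Part 1 had 806 participants randomised 1:1, and protocol section 2.3.2 reports no safety concerns, including for AEs of special interest. An otilimab-only AE at 5% would have been about 20 v 0 there (0.05 × 403). That makes the scenario less likely but does not exclude it, since Part 2 removes the upper age limit.

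**Conclusion.** The point holds as a gap in descriptive safety reporting. Within the scope that section 4.5.2 sets for itself, an AE that is common in one arm and absent in the other receives no relative risk, no interval and no position in the ordering. That is the SAP's only between-arm AE comparison. At the planned 173 per arm this begins at 9 v 0, while 9 v 1 is estimated.

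The conclusion rests on the 5% threshold, the Wald method and the absence of a zero-cell rule in the SAP. It does not depend on how *either* is read. The arm size assumes the planned 346 split equally. The Fisher p-values are descriptive and show only that such a contrast is unlikely to be chance. No endpoint, hypothesis test or decision rule changes, and the counts remain visible in the incidence tables.

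**What to change.** In Part 2 SAP section 4.5.2:

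1. Replace the exclusion with a rule that every AE at 5% or more in either arm stays in the comparative display, with n/N per arm and a risk difference with a score-type 95% interval (Newcombe or Miettinen-Nurminen). Both intervals are defined when one arm has no events.
2. Keep the relative risk and its ordering. Show one-arm-zero AEs at the extreme of the plot as an open-ended bar from the finite score bound (about 2.4 for 9 v 0). Ranking by risk difference instead is optional.
3. In the same edit, reconcile the Wald intervals named for the relative risks with the exact interval named for the plot, and state the method used.

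The cost is a few SAP sentences and an option in the AE display program. No new data are needed.

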4.5.2.1. Adverse Events of Special Interest

The following will be considered adverse events of special interest (AESI) for the purpose of analyses:

- Cytokine release syndrome (CRS)
- Serious hypersensitivity reactions
Note: these will be adjudicated by the SRT.
- Infusion site reactions
- Neutropenia \geq Grade 3 ($< 1.0 \times 10^9/L$)
- Serious infections

Listings of event characteristics will be provided for each AESI respectively. For AESIs with more than 8 events a summary of event characteristics will be provided for each AESI respectively, including number and percentage of participants with any event, number and percentage of events, maximum intensity, outcomes and the action taken for the event. The worst-case approach will be applied at participant level for the maximum intensity, *i.e.* a participant will only be counted once as the worst case from all the events experienced by the participant.

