4.5.2.3. Subgroup Analyses

The following subgroups will be included in the safety subgroup analyses: sex, clinical status at Baseline, and age as defined in Section 4.1.6.2.

For the Safety population and all subgroups defined above, summaries of common AEs, common SAEs (see Section 4.5.2), AESIs, and all AEs and SAEs by PT group (see Section 4.5.2.2) and PT will be presented.

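### Part 2 plans no between-arm estimate for any adverse event of special interest, at any event count

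*SAP*

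**What the plan says.** Protocol 7.4.7 names five AESIs, which it introduces as potential risks of otilimab: cytokine release syndrome (CRS) not related to COVID-19, serious hypersensitivity reactions, infusion site reactions, neutropenia of grade 3 or worse, and serious infections.

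For these, Part 2 SAP 4.5.2.1 provides two displays. "Listings of event characteristics will be provided for each AESI respectively", whatever the count. Then, "For AESIs with more than 8 events a summary of event characteristics will be provided for each AESI respectively". That second display covers counts and percentages of participants and of events, worst intensity, outcome and action. No risk difference, relative risk or interval is mentioned in either display.

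The one planned comparison of AEs between arms is in SAP 4.5.2: "Unadjusted Relative risks with Wald confidence intervals based on observed frequencies", restricted to common AEs (at least 5% in either arm). The section adds: "Relative risks will not be calculated if there are no events in either of the two treatment arms being compared".

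Other displays have no such threshold. In 4.5.2, "The frequency and percentage of AEs (all intensities) will be summarized and displayed in two ways" (by preferred term, and by system organ class and preferred term), and all SAEs are tabulated. Section 4.5.3.2 counts participants whose neutrophil grade rises to 3 or 4. Section 4.5.2.3 promises further summaries: "For the Safety population and all subgroups defined above, summaries of common AEs, common SAEs", followed by AESIs, without repeating the 8-event condition.

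**The concern.** The AESIs are the risks the protocol singled out in advance, and Part 2 is described as confirmatory and Phase 3, in participants aged 70 or above with no upper limit. For these categories a reader of the report will want the difference between arms and the size of difference the data can exclude. The plan produces neither. The relative-risk rules are built for common events, while the protocol's benefit-risk conclusion for Part 2 expects a very low risk of CRS, so at least that category is expected to fall outside them. A report could then say that no AESI difference was seen without having estimated one.

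The AESIs also get less than other groups of interest. For pneumonia, sepsis, opportunistic infections, thromboembolic events and pulmonary embolism, SAP 4.5.2.2 promises group-level summaries with each participant counted once and no event threshold.

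**Working it through.** **Inputs.** Part 2 sample size 346, 80% power, 45% versus 60%, one-sided 2.5% (SAP 5); 1:1 allocation (protocol 8.2); AESI table threshold of more than 8 events (SAP 4.5.2.1); relative-risk threshold of 5% in either arm and the no-events rule (SAP 4.5.2). The size of the safety set is not given. About 173 per arm is assumed.

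**Step 1: reproduce the plan's sample size.** With pooled variance under the null and no continuity correction:

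n per arm = [1.960·√(2 × 0.525 × 0.475) + 0.842·√(0.45 × 0.55 + 0.60 × 0.40)]² / 0.15² = (1.384 + 0.588)² / 0.0225 ≈ 172.8, rounded up to 173.

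This gives 346 in total, as stated, so 173 per arm is a fair denominator.

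**Step 2: the 5% rule in participants.** 8/173 = 4.62%, below 5%. 9/173 = 5.20%, above it. An arm needs 9 participants with the event. With 175 per arm (the protocol's approximate 350) the answer is again 9.

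**Step 3: apply the rules, one event per participant.**

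| Otilimab v placebo | Rates | Descriptive AESI table in 4.5.2.1? | 5% rule met? | Relative risk? | Fisher p (two-sided) |
|---|---|---|---|---|---|
| 6 v 0 | 3.5% v 0% | No | No | No | 0.030 |
| 8 v 0 | 4.6% v 0% | No | No | No | 0.007 |
| 8 v 1 | 4.6% v 0.6% | Yes | No | No | 0.037 |
| 12 v 0 | 6.9% v 0% | Yes | Yes | No | 0.0004 |

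The 8 v 1 row shows that passing the 8-event threshold adds a descriptive table and no estimate. The 12 v 0 row shows that passing the 5% rule as well still yields nothing if one arm is empty. The no-events sentence could be read as meaning that both arms are empty. That reading does not help, because with a zero cell the relative risk is infinite or zero and its Wald interval is undefined.

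**Step 4: what could be reported.** For 8 v 0 the risk difference is 8/173 − 0 = 4.6 points, with a 95% interval of 2.4 to 8.9 (Miettinen-Nurminen) or 1.5 to 8.9 (Newcombe). For 6 v 0 it is 3.5 points, 1.3 to 7.4 (Miettinen-Nurminen). For 12 v 0 it is 6.9 points, 3.3 to 11.7 (Newcombe). All are computable with a zero cell.

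**Step 5: how often the thresholds would bite.** The documents give no AESI rates, so these are assumed. Let X1 ~ Binomial(173, p1) on otilimab and X0 ~ Binomial(173, p0) on placebo.

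| Assumed p1 v p0 | P(X1 + X0 ≤ 8): no descriptive table | P(X1 ≤ 8)·P(X0 ≤ 8): 5% rule not met | No relative risk, counting an empty arm as well |
|---|---|---|---|
| 4% v 0.5% | 62% | 74% | 85% |
| 3% v 0.5% | 84% | 92% | 95% |

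The first column concerns only a descriptive table. The other two concern the estimate.

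**The case against.** The strongest reply is that nothing is concealed. Protocol 7.4.7 requires AESIs to be reported as AEs or SAEs, so each one enters tables without an 8-event or 5% threshold. Serious hypersensitivity and serious infections appear among the SAEs, neutropenia in the laboratory grade table, and much of serious infection in the groups of 4.5.2.2. A reader might infer from 4.5.2.1 that a rare AESI is reported as a listing and nothing else, so that an 8 v 0 split would go unseen. The documents do not support that. The listing-only outcome applies within 4.5.2.1, and 4.5.2.3 promises AESI summaries as well.

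A reader might also infer that the 8-event rule removes the between-arm estimate. It does not, because the table it controls is descriptive at every count. It would likewise be too strong to call these known harms, since the protocol calls them potential risks, or to say that no component could ever get a relative risk. A single AE reaching 5%, with events in both arms, would get one.

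Finally, protocol 8.4.5 says that no formal safety hypotheses will be tested, and an IDMC reviews unblinded safety data.

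All of this stands, and it limits the point to estimation at category level. The point itself survives for two reasons. First, tables by preferred term do not give the AESI count. Serious hypersensitivity is adjudicated by the safety review team, CRS is defined by worsening within 6 hours of the start of infusion and not related to COVID-19, and participants cannot be added across terms without double counting. Second, none of these tables carries an interval. Protocol 8.4.5 is no obstacle, since it allows statistical analyses where appropriate and an interval is not a hypothesis test.

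**Conclusion.** The point holds as a gap in estimation, not as concealment. No between-arm estimate is planned for any of the five AESI categories. The causes are that none is specified in 4.5.2.1, that relative risks are limited to AEs at 5% or more, and that they are unavailable with an empty arm. A split of 8 v 0, a difference of 4.6 points with an interval excluding zero, would be visible in counts by preferred term but would have no category-level estimate. So would 12 v 0. Sections 4.5.2.1 and 4.5.2.3 also leave unclear whether category counts appear at 8 events or fewer, and must be reconciled.

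The figures assume about 173 dosed per arm and one event per participant. The SAP threshold counts events, so 8 events could come from fewer than 8 participants. The probabilities in step 5 also rest on assumed event rates and only illustrate the scale.

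**What to change.** In Part 2 SAP 4.5.2.1, for each of the five AESI categories and whatever the count, report the number and percentage of participants by arm, and the risk difference (otilimab minus placebo) with a 95% Miettinen-Nurminen interval or another interval that is valid with a zero cell. State that this is estimation without a hypothesis test, consistent with protocol 8.4.5. Keep the listings. Keep the more-than-8-events condition only for the detailed breakdown of intensity, outcome and action taken. Amend 4.5.2.3 so that both sections say the same about when AESI counts appear.

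The cost is one five-row table from data already collected. For very rare events the intervals will be wide, which correctly shows how little the trial can exclude.
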